It is possible that the intervention may bring up strong emotions for the participants; so too might the administration of the ACE survey which will be part of the preliminary data collection (more below). To mitigate this potential, the PI will caution students that this may occur and emphasize the importance of self-care and knowing one's own limits with the intervention. Immediate referrals regarding suicidality, self-harm, depressive thoughts, etc. will be directed to the school nurse. If needed, referrals for additional, outside treatment will be provided as determined by school officials and/or requested by the participant and/or the participant's legal guardian(s). It will also be explained to participants that this study is not designed to be a clinical/psychological intervention but rather an academic intervention, so students that need additional mental health supports will be referred to appropriate outside agencies.

Additional resources for outside assistance will be shared with participants and participant parents/guardians on the assent/consent forms, listing the following avenues for additional help:

- Talking with someone who you can trust
- Calling 911, your doctor or other healthcare provider
- Going to an Emergency Room
- Calling [name] to talk with a crisis worker for free
- Texting 741741 to text with a counselor for free

Visiting NowMattersNow.org to learn skills for dealing with thoughts of suicide

**Aim 1:** Foster a partnership with a rural southwestern Montana school and test the feasibility of implementing a trauma-informed yoga intervention.

For this pilot study, feedback will be gathered from the school district, teachers, and students from the focus group via conversations and/or email communications to determine the level of burden from the various assessment instruments and participation in the pilot; plans and identified needs for this study are ongoing with the school district and the PI. Retention and satisfaction of participants, as measured by survey instrumentation) from year one will indicate the feasibility of an ongoing partnership with the school district, determine possible expansion to the middle school in year two, and will assess both students' and teachers' perception of value of the intervention. Because this is a feasibility study, no control group will be utilized, and the focus of the project will be to examine pre and post survey results and cortisol levels.

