To allow all who are interested to participate in the study, the focus of this project will primarily be to determine feasibility of the intervention; therefore, no control group will be utilized, and the focus of the feasibility trial will be to examine pre and post survey results and cortisol levels. Volunteers will participate in the intervention for 8 weeks. During the intervention phase, the participation goal for each student will be to attend 75% or more of the intervention sessions (attendance will be recorded by the yoga instructor).

After students volunteer for program participation, to establish a baseline for participants, students will be given the ACE screening instrument/ toolkit of pre-surveys and then begin the 8-week intervention. Students will be administered cortisol testing at the beginning of weeks 1 and 4 and the conclusion of week 8 during the intervention, each time prior to the yoga session, and they will complete the post surveys at the conclusion of week 8. At each of the three testing periods, students will provide a saliva sample to the school nurse or PI, to be deidentified (using a code key system) before analysis by the CAIRHE Translational Biomarkers Core Lab at MSU. Testing will use the Abcam (ab154996) cortisol in vitro competitive ELISA (Enzyme-Linked Immunosorbent Assay) kit designed for the accurate quantitative measurement of cortisol in saliva (sensitivity 0.12 ng/ml). Deidentified cortisol data will be returned to the PI for re-identification using the code key. Comparisons using paired t tests between pre and post-surveys will be utilized to determine program efficacy, and any changes in cortisol levels throughout the duration of the program will be analyzed to assess any trends and whether this is a useful measure for the next study phase.

**Aim 3:** Use the preliminary data to modify (as needed) year two of the study for expansion to middle level students and/or increasing the number of high school participants.

This study will utilize descriptive statistics for pre- and post-interventions and analysis of cortisol levels throughout the program to determine the efficacy the intervention.

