## **Statistical Analysis Plan**

Quantitative analyses between pre-intervention (T1) and post-intervention (T2) scores will be utilized for participants who completed the measures at both time points using a paired samples t-test or a Wilcoxon signed rank test with continuity correction for non-normal distributions.

Next, analyses of covariance (ANCOVA) following treatment completion will be used to evaluate whether there are significant post-treatment differences in student-reported symptoms between children with low (0-1), moderate (2-3), and high (4+) ACE scores, with pre-intervention student-reported symptoms and attendance rate as the covariate. The outcome measures to be used in these analyses are the GAD-7, PHQ-A, SDQ, and the SDQ subscales. ANCOVA is the clearest and most straightforward analysis to address each of the analytic goals.

Salivary cortisol samples will be deidentified (using a code key system) before analysis by the CAIRHE Translational Biomarkers Core Lab at Montana State University. Testing utilized the Abcam (ab154996) cortisol in vitro competitive ELISA (Enzyme-Linked Immunosorbent Assay) kit designed for the accurate quantitative measurement of cortisol in saliva (sensitivity 0.12 ng/ml). Comparisons using paired t tests between pre and post-surveys will be utilized to determine program efficacy, and any changes in cortisol levels pre and mid-intervention were analyzed to assess any trends and aided in the decision-making process for whether to continue using this measure for the next study phase.

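### The SAP's only sentence on cortisol change stops at mid-intervention, while the protocol plans a pre-post comparison and an analysis over the whole program

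*Combined protocol and SAP*

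**What the plan says.** The Methods section is consistent on cortisol. Under Aim 2, the list of assessment measures has cortisol taken before, during and after the program. The schedule reads "Students will be administered cortisol testing at the beginning of weeks 1 and 4 and the conclusion of week 8", and each sample is to be taken "each time prior to the yoga session". The analysis paragraph under Aim 2 plans descriptive statistics comparing cortisol before and after the intervention. Later under Aim 2, changes over the full course of the program are to be examined for trends and to judge whether the measure is worth keeping. Aim 3 repeats the whole-program analysis and ties it to efficacy.

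On importance, Aim 1 states that "the focus of the project will be to examine pre and post survey results and cortisol levels", and Aim 2 says nearly the same: "the focus of the feasibility trial will be to examine pre and post survey results and cortisol levels".

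The Statistical Analysis Plan has one paragraph on cortisol. It covers deidentification and the assay, and then says that "any changes in cortisol levels pre and mid-intervention were analyzed to assess any trends and aided in the decision-making process" on whether to continue with the measure. It mentions no week-8 or other post-intervention cortisol sample. The SAP's general rule for before-after comparisons comes earlier and does not name cortisol: "Quantitative analyses between pre-intervention (T1) and post-intervention (T2) scores will be utilized" "for participants who completed the measures at both time points".

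**The concern.** The SAP's cortisol sentence closely follows the Aim 2 trend sentence in the Methods, but the window has shrunk from the whole program to the stretch from baseline to mid-intervention. The verbs have also moved into the past tense. No reason is given, and nothing in the SAP withdraws the Methods text. The two sections belong to the same combined document, so both appear to be in force.

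An analyst who follows the SAP's cortisol paragraph as written would not produce the before-after comparison that the Methods promise. The SAP also says that the early change helped decide whether to keep cortisol as a measure. If readers take that early change for a before-after result, they will credit it with more exposure to the intervention than the students had at that sample.

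**Working it through.** The documents give no sample-size or precision figure for cortisol, so there is no stated result to reproduce. The check is a comparison of texts and a count of sessions.

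**Time points**

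- Methods, schedule: three samples (start of week 1, start of week 4, end of week 8).
- Methods, Aim 2 analysis paragraph: before versus after, descriptive. This needs week 1 and week 8.
- Methods, Aim 2 trend sentence and Aim 3: the whole program. This needs all three samples.
- SAP, cortisol paragraph: baseline and mid-intervention only.

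The Methods statements fit together, because a before-after comparison is part of an analysis of all three samples. The mismatch is between the SAP and the Methods. Three samples give 3 × 2 / 2 = 3 pairwise contrasts. The SAP's cortisol sentence covers one of them, week 1 to week 4, if mid-intervention means week 4. Week 1 to week 8 and week 4 to week 8 are not covered.

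**Sessions behind the mid-intervention sample**

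Inputs, all from Methods: two sessions a week for 8 weeks; second sample at the start of week 4, before the session; and an attendance target under which "the participation goal for each student will be to attend 75% or more of the intervention sessions". Assumption: mid-intervention means the week-4 sample, the only one scheduled between the first and the last.

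- Planned sessions: 2 × 8 = 16.
- Sessions before the week-4 sample: at most 2 × 3 = 6, and 6/16 = 37.5%.
- Sessions after it: 16 − 6 = 10, and 10/16 = 62.5%.
- Sessions needed to meet the attendance target: 0.75 × 16 = 12. At the week-4 sample a student can have had at most 6/12 = 50% of these.
- Week-8 sample, if taken before the last session: up to 16 − 1 = 15 sessions.

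The contrast named in the SAP thus reflects at most 6 sessions, against up to 15 for the contrast promised in the Methods.

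**Does the general rule fill the gap?**

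The rule compares T1 with T2, which are pre- and post-intervention. It could be stretched to cortisol, because the Methods list cortisol among the assessment measures. But it speaks of scores and does not name cortisol, which has its own paragraph and its own window. If the rule did apply, it would call for a paired test where the Methods plan descriptive statistics. The analysis of all three samples would still be missing from the SAP.

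**The case against.** The strongest reply is that this is silence rather than contradiction. The SAP does not say that week 8 is excluded. Its sentence can be read as reporting a step already taken, an early look that fed a decision about the measure, while the before-after plan in the Methods still stands. That reading is possible. It is weakened by how closely the sentence tracks the Methods sentence with only the window and tense changed, and the SAP does not state it. So the reader still cannot tell what will be reported at week 8.

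A second reply is that cortisol matters little here. Much of this stands. The Methods give feasibility as the primary focus and apply the term primary to the survey assessments. The Aim 2 sentence attaches efficacy to the paired survey tests, not to cortisol. The link from cortisol to efficacy rests on the Aim 3 sentence alone. Still, cortisol is named within the study's focus and is used to decide what the next phase measures.

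A reader might go further and infer that week-8 samples were never taken, or that the window was narrowed because of what the results showed. The documents support neither. The past tense suggests that some cortisol data had been examined when the sentence was written, but the text gives no date and no cause.

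**Conclusion.** The concern holds as a conflict between the SAP and the Methods over which cortisol time points are analysed, and it should be fixed. The Methods sections do not conflict with one another. The SAP's cortisol text taken alone omits the promised before-after comparison and rests on a sample preceded by at most 6 of 16 sessions (37.5%). This count assumes that mid-intervention is the week-4 sample and that sessions run twice weekly as planned. A change up to that sample should not be presented as a pre-post result.

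A reader might also infer that the two windows gave different answers, or that a study conclusion changed. The documents contain no cortisol results and no information on how cortisol changes over the sessions, so neither can be shown. What is established is an unexplained omission affecting a descriptive measure in an uncontrolled feasibility study of 30 students.

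**What to change.** Reconcile the SAP's cortisol paragraph with the Methods. First state whether the week-8 samples were collected and assayed.

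- **If they were:** amend the SAP to say that cortisol will be summarized descriptively at weeks 1, 4 and 8, and that within-student change from week 1 to week 4 and from week 1 to week 8 will be reported, with the number of students sampled at each time. Confidence intervals are optional, since the Methods plan a descriptive analysis.
- **If they were not:** state how many are missing and why, report the absent before-after comparison as a departure from the protocol, and limit the cortisol conclusion to change up to mid-intervention.

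In either case, define mid-intervention as a scheduled sample, date the amendment, and say whether cortisol results had been seen when it was written.

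The cost is small: SAP wording and one table with three time points if the data exist, or a short disclosure if they do not. No new data are needed.
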